8 SAFETY MANAGEMENT

8.1 Clinical Adverse Events

Clinical adverse events (AEs) will be monitored throughout the study.

8.2 Adverse Event Reporting

Since the study procedures are not greater than minimal risk, SAEs are not expected. If any unanticipated problems related to the research involving risks to subjects or others happen during the course of this study (including SAEs) they will be reported to the IRB in accordance with CHOP IRB SOP 408: Unanticipated Problems Involving Risks to Subjects. AEs that are not serious but that are notable and could involve risks to subjects will be summarized in narrative or other format and submitted to the IRB at the time of continuing review.

8.3 Medical Emergencies

As hospitalization for medical stabilization can occur during routine treatment, hospitalization will not be considered an SAE. A summary of all hospitalizations for medical stabilization will be provided at the time of continuing review.

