1 BACKGROUND INFORMATION AND RATIONALE

Anorexia Nervosa (AN) is a serious eating disorder characterized by restriction of food intake and reduction of body weight below what is healthy or expected for someone of the same age and height. AN has the highest mortality rate of all psychiatric disorders^{1,2} and is associated with significant morbidity.¹ AN often begins during adolescence³ and early intervention is key in order to prevent a chronic, unremitting course of the disorder.⁴ To date, there is only one intervention with substantial empirical support for the treatment of AN in adolescents: Family Based Treatment.^{5,6} In FBT, parents are essential to treatment and are charged with the task of re-nourishing their starving child. The effectiveness of FBT has established the importance of the family in treatment and empowered parents to play an active role in treatment.^{7,8}

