6.3.2 Safety Analysis

All participants enrolled will be included in the safety analysis. Frequency of hospitalization and referral to a higher level of care will be summarized. Differences between those who need hospitalization and those who do not over the course of the study will be explored and reported.

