9.4.1.2 Continuous Quality Assurance and Quality Control Procedures (QA/QC)

QA/QC will be implemented to ensure compliance with study requirements in areas including recruitment and data collection. Quality control activities will be performed regularly on all electronic data and participant files to ensure that all data collected is complete and accurate. These will include the reconciliation of data forms, verification of codes and labels, and careful

review of each individual data field for omission and errors. All neuropsychological assessments will be scored twice for reliability and all data will be entered into the database twice to ensure accuracy.

In terms of day-to-day safety monitoring, the therapist will track weight, eating disorder symptom information, and closely monitor suicidality, self-harm, and other concerns. If a therapist becomes aware of suicidal or homicidal ideation or serious self-harm behavior, the adolescent will undergo a comprehensive assessment of plan and intent and the necessary precautions will be taken to insure safety or medical attention as appropriate. Standard clinic practice is for therapists to make judgments about mental status, global symptom severity, and symptom improvement at each visit and this information becomes part of patients' permanent clinical records. Participants in the study will have CHOP behavioral health emergency numbers.

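### Section 8.3 exempts hospitalization from SAE status without qualification, although its reason and its substitute summary cover only medical stabilization

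*Combined protocol and SAP*

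**What the plan says.** Section 8.3 (Medical Emergencies) contains two sentences. The first sets the rule: "As hospitalization for medical stabilization can occur during routine treatment, hospitalization will not be considered an SAE". The second sets the substitute reporting: "A summary of all hospitalizations for medical stabilization will be provided at the time of continuing review".

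Section 8.2 (Adverse Event Reporting) opens with "Since the study procedures are not greater than minimal risk, SAEs are not expected". It sends unanticipated problems related to the research, SAEs among them, to the IRB. For lesser events it says "AEs that are not serious but that are notable and could involve risks to subjects will be summarized in narrative or other format", with submission at continuing review.

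Section 6.3.2 (Safety Analysis) says "All participants enrolled will be included in the safety analysis" and "Frequency of hospitalization and referral to a higher level of care will be summarized".

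Section 9.4.1.2 tells therapists to "closely monitor suicidality, self-harm, and other concerns". Section 9.4.1.3 lists the parts of the DSMB report. Adverse events have a part, but hospitalizations and higher-level-of-care referrals are not named.

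**The concern.** The reason given in 8.3 is that medical stabilization is an ordinary part of treating this illness. That supports exempting that kind of admission. It does not support exempting an admission after self-harm, a psychiatric admission or an unrelated emergency. It cannot apply at all to a parent, and parents are enrolled with their own eligibility criteria and receive CRT in one arm.

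The admissions that would be lost are ones the protocol itself foresees, since therapists are told to watch for suicidality and self-harm. If staff follow the literal text, the SAE count is low partly by definition, and an imbalance between arms in such admissions could be missed while the DSMB can still act. If some staff read the sentence narrowly and others literally, classification depends on who fills in the form. Either way the safety record is harder to interpret.

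**Working it through.** No figure is involved, so the check compares the wording of the sections.

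**Step 1: scope within 8.3.** The first clause is limited to medical stabilization. The rule that follows is not. The next sentence restores the limit for the summary. The substitute report is therefore narrower than the exemption as written.

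| Kind of admission | Covered by the stated reason | Exempt under the rule, read literally | In the 8.3 summary |
|---|---|---|---|
| Medical stabilization of anorexia nervosa | yes | yes | yes |
| Psychiatric or self-harm | no | yes | no |
| Other cause, adolescent or parent | no | yes | no |

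The rule takes in three kinds, and the reason and the summary one each. That leaves 3 − 1 = 2 kinds with neither a justification nor a place in the 8.3 summary.

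**Step 2: does another section bring the two kinds back in?** The supplied text has no SAE definition that does so. Section 4.6 separates hospitalization for medical stabilization, after which the adolescent may return to the trial, from referral to a higher level of care such as inpatient treatment, which ends trial treatment. Section 4.7 names higher-level referral in a similar way. The protocol thus recognises different kinds of admission, but neither section says how any of them is classified for SAE purposes.

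**Step 3: where would such an admission still appear?**

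- *Section 6.3.2.* Its frequency of hospitalization has no limit by cause. It is an aggregate, with no stated timing, breakdown by cause or arm, or DSMB recipient.
- *Section 8.2, first route.* An event judged to be an unanticipated problem related to the research goes to the IRB whether or not it is an SAE. An admission judged unrelated or anticipated does not qualify.
- *Section 8.2, second route.* A non-serious event judged notable is summarized at continuing review. This rests on a judgment about each event.
- *Section 9.4.1.* Adverse events associated with participation go promptly to the principal investigator and the coordinator.
- *Section 9.4.1.3.* Every DSMB report has an adverse-event part, which could include the admission. Nothing requires that it does.
- *Section 4.7.* Events learned of after completion or withdrawal are recorded if serious and related, so this route depends on the classification that 8.3 removes.

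**Step 4: timing of board review.** Section 9.4.1.3 sets four DSMB meetings: before the start, at 6 and at 12 months after recruitment opens, and after all treatment has ended. Two of the four fall between the start of recruitment and the end of treatment. An admission left out of those two reports may not reach the board until treatment is over.

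**Result.** The literal text takes two unjustified kinds of admission out of SAE status on the ground of hospitalization. The remaining routes are aggregate, conditional or discretionary.

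**The case against.** The strongest reply is that the unqualified word is shorthand. The phrases before and after it in 8.3 both specify medical stabilization, and on that reading the exemption and the summary match exactly. Sections 4.6, 5.3 and 6.3.2 also tend to keep hospitalization apart from referral to a higher level of care, so a psychiatric inpatient stay may never have been meant. This stands as a plausible account of intent. It does not settle how staff will apply the rule, because no definition in the supplied text confirms it.

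It is also fair that 8.3 removes hospitalization as a ground for seriousness and no more. A suicide attempt that is serious on another ground is not expressly exempted.

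A reader might infer several stronger things that the documents do not support:

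- *That other-cause admissions are summarized nowhere.* Section 6.3.2 counts hospitalization without regard to cause, and 8.2 provides for notable non-serious events.
- *That they have no route to the DSMB.* Adverse events are part of every report. The board also approves a safety monitoring and reporting plan, and a charter is to be written; neither is in the supplied text. What can be said is that nothing supplied assures inclusion.
- *That reporting lags by about 12 months.* The yearly report in 3.1.3 concerns sessions held remotely, and the DSMB also meets at 6 months.
- *That "Since the study procedures are not greater than minimal risk, SAEs are not expected" contradicts "AN has the highest mortality rate of all psychiatric disorders".* The first rests on the risk of study procedures and the second describes the disease. A list of expected serious events would be a preference, not a correction.

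Finally, assessing parents' admissions will bring in some events unrelated to the trial. That is a real but small burden.

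**Conclusion.** The point holds as a defect in a stated rule: the exemption in 8.3 is broader than its reason and broader than the summary that replaces SAE reporting. On the literal reading, two of three kinds of admission lose SAE status on the ground of hospitalization without justification and are outside the 8.3 summary. They remain in the aggregate of 6.3.2 and may surface under 8.2 or in the DSMB's adverse-event section, but event-level serious reporting is not assured.

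This rests on two conditions: that staff apply the sentence as written, and that no SAE definition outside the supplied text overrides it. The text does not prove an intent to exempt every cause. No admission rates are given, so neither the number of events affected nor the chance of missing an imbalance between arms can be calculated. No efficacy endpoint or estimate is affected.

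**What to change.** - **Section 8.3.** Confine the exemption expressly to hospitalization for medical stabilization of anorexia nervosa. State that any other admission of an enrolled adolescent or parent is assessed and reported as a serious event under 8.2.
- **Reconciliation.** Align 8.3 with 4.6 (which kinds of admission are distinguished), 6.3.2 (what is counted), 8.2 (who receives a serious event, including one judged unrelated) and 9.4.1.2 (the suicidality and self-harm that therapists monitor). The same kind of admission should then be classified the same way throughout.
- **Section 9.4.1.3.** Include hospitalizations and higher-level-of-care referrals, by randomised arm, in the adverse-event part of the DSMB report.

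The cost is a wording amendment, a few more SAE forms and a higher reported SAE count. Sample size, endpoints and efficacy analyses do not change.

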9 STUDY ADMINISTRATION

9.1 Treatment Assignment Methods

9.1.1 Randomization

Procedures for randomization were described in Section 3.2.

9.1.2 Blinding

Research assistants who assess adolescents at each time point will not be aware of their study condition.

9.2 Data Collection and Management

All data (with the exception of DKEFS, WASI, BRIEF, and BASC as these have standardized forms) will be stored in RedCap. Scores from these standardized forms will be entered into RedCap to ensure all data is in the same place.

All participants will be given a unique study ID and all study information will be coded using this number (in RedCap and on standardized forms). The master list linking participants with their numbers will be stored in a separate RedCap file that only members of the research team will have access to.

RedCap data will be downloaded weekly and stored in a password protected file on the secure research server. Only the CRC and PI will have the password. This is for backup.

Audio/video files of treatment sessions will be stored on the research server and destroyed after study end. These are necessary to ensure treatment fidelity. Only study staff involved in the project will have access to these files.

Data will remain coded until all study procedures are complete and initial findings have been published. After 6 years, the list linking study IDs to participants will be destroyed. Remaining data will be retained indefinitely.

9.2.1 Data sharing

Per NIH requirements, data will be shared via the National Database for Clinical Trials related to Mental Illness. Within 3-months of the award, the PI will complete a NIMH Data Repositories Data Submission Agreement. Per guidelines, data will be shared in two tiers: raw data while the study is on-going and analyzed data with publication of results/after the reward period. Once a manuscript is published, all analyzed data will be submitted. Data will include descriptive/raw day from questionnaires, demographic data, and data abstracted from the medical chart. We will also include raw and standard scores for the neuropsychological assessments used in the course of this study. Per requirements, raw data will be submitted bi-annually, starting 6 months after project begin. Given the novel aspect of behavioral data (Howe's Grocery and Buffet Challenge), we will work with staff in order to ensure appropriate and smooth submission of data. Video recordings of the buffet challenge will not be submitted. Additionally, video recording of the clinical interviews will not be submitted. We will ensure that all participants will have a Global Unique Identifier and each data set will be associated with the appropriate publications.

The PI will encourage anyone who is interested in accessing the data to use the National Database. As some researchers may not have access to or wish to access the National Database,

we will make a cleaned, de-identified data set and codebook available for request 6 months after complete study end and the publication of initial manuscripts. The data will be made available to other researchers under a data sharing agreement that will provide for a commitment to using the data for research purposes and to destroying or returning the data after analysis are completed. Researchers can request the data from the PI via email. Requests are necessary given the nature of the data; although it will be de-identified, it will contain sensitive health information about the participants.

9.3 Confidentiality

All data and records generated during this study will be kept confidential in accordance with Institutional policies and HIPAA on subject privacy and that the Investigator and other site personnel will not use such data and records for any purpose other than conducting the study.

No identifiable data will be used for future study without first obtaining IRB approval. The investigator will obtain a data use agreement between the provider (the PI) of the data and any recipient researchers (including others at CHOP) before sharing a limited dataset (PHI limited to dates and zip codes).

9.4 Regulatory and Ethical Considerations

9.4.1 Data and Safety Monitoring Plan

Data and safety will be monitored on multiple levels. The PI has primary responsibility of study oversight and will meet with study staff regularly to monitor study progress, safety issues, recruitment progress, attrition, and data quality. [name] will meet as needed with the Medical Safety Officer to review new patients or any concerns.

We will monitor participants for the occurrence of any adverse events associated with data collection and participation and will report these events as directed by the institutional IRB and adverse event (AE) reporting policies. Events will be reported promptly to [name] (PI) and the study coordinator who will make provisions to respond appropriately, ensuring referral to medical/professional resources, as needed.

9.4.1.1 Breach of Confidentiality.

The PI will ensure that all members of the study team have completed all mandatory confidentiality statements and research ethics trainings and that data have been handled and stored properly. Annually, research staff will be required to sign a statement acknowledging their receipt and understanding of the confidentiality requirements and pledging to maintain confidentiality of the data to which they have access. If a breach of confidentiality is identified, the PI will immediately meet with IRB and data security leadership to review and identify how the breach occurred and to review and discuss steps to prevent future problems with ensuring participant confidentiality.

9.4.1.2 Continuous Quality Assurance and Quality Control Procedures (QA/QC)

QA/QC will be implemented to ensure compliance with study requirements in areas including recruitment and data collection. Quality control activities will be performed regularly on all electronic data and participant files to ensure that all data collected is complete and accurate. These will include the reconciliation of data forms, verification of codes and labels, and careful

review of each individual data field for omission and errors. All neuropsychological assessments will be scored twice for reliability and all data will be entered into the database twice to ensure accuracy.

In terms of day-to-day safety monitoring, the therapist will track weight, eating disorder symptom information, and closely monitor suicidality, self-harm, and other concerns. If a therapist becomes aware of suicidal or homicidal ideation or serious self-harm behavior, the adolescent will undergo a comprehensive assessment of plan and intent and the necessary precautions will be taken to insure safety or medical attention as appropriate. Standard clinic practice is for therapists to make judgments about mental status, global symptom severity, and symptom improvement at each visit and this information becomes part of patients' permanent clinical records. Participants in the study will have CHOP behavioral health emergency numbers.

9.4.1.3 Data and Safety Monitoring Board

This study will be conducted under the guidance of a Data Safety and Monitoring Board (DSMB). The DSMB will act in an advisory capacity to monitor participant safety, evaluate the progress of the study, and review procedures for maintaining the confidentiality of data and the quality of data collection, management, and analyses. The Board will be led by a chair and at least 3 additional members. Board members will have expertise in an area relevant to the study aims, examples are: adolescent health research, behavioral treatment, neuropsychology/neurocognition, treatment implementation, statistical analysis, adolescent development, and/or eating disorders. DSMB members will have no direct involvement with the study investigators or intervention. The board will meet 4 times during the study. Board members will review study progress, data quality, and participant safety. The first meeting will occur prior to initiation of study activities to review and approve the study protocol and safety monitoring and reporting plan. Subsequent meetings will occur 6 months after the start of study recruitment, 12 months after the start of study recruitment, and again after all treatment has ended and data analysis has begun. Ideally, all meetings will be in person, however, remote participation (i.e., via Skype or Zoom). A detailed DSMB Charter will be developed that provides a detailed list of DSMB responsibilities.

The DSMB will receive a data and safety monitoring report at each scheduled meeting. This report will include the following sections: Overview of DSMB, Study Status, Study Recruitment, Study Enrollment, Study Randomization, Participant Characteristics, Study Data Collection, Regulatory Compliance, Adverse Events and Protocol Deviations, Quality Control and Data Management, Data Analysis, Sample Size and Power Analysis, Outcome Data, Recent Publications of Relevance, and Challenges and Resolutions. In these reports, data and discussion will be confidential and participant identities will not be revealed.

9.4.2 Risk Assessment

Risks are not greater than minimal. The treatments being used in this study are close to routine care and do not carry a great risk of harm.

Completion of the measures can be burdensome, however, we have taken step to reduce the burden and any fatigue by breaking up questionnaire completing with neuropsychological

testing. Participants are allowed to take breaks as needed and are given time to eat snacks. A similar procedure has been used in prior research by the PI and was tolerated well by families.

The buffet challenge may be difficult for adolescents at the beginning of treatment and videotaping may be stressful for the adolescent. Parents will be made aware of the challenge and will be able to provide the adolescent with snack after the buffet is complete. As the initial clinical interview occurs at the end of intake, any concerns will be able to be addressed with the therapist.

9.4.3 Potential Benefits of Trial Participation

FBT is the gold standard of treatment. Families will receive guidance and support in refeeding their child. Most adolescents should gain weight and experience a reduction in eating disorder symptoms. CRT is highly acceptable and has been shown to decrease drop out from treatment.

9.4.3.1 Indirect benefit

More treatments for anorexia are needed, particularly for those who do not fare well in FBT. This study investigates whether or not CRT can be a viable augmentation to treatment and for whom (parents or child) it has the most benefit.

9.4.4 Risk-Benefit Assessment

Risks are minimal. All adolescents will receive family-based treatment – the most recommended treatment for adolescents with AN. Two groups will receive an additional session of CRT each week. Adolescents will be required to have medical care during the course of the study. If they are not improving, recommendations for a higher level of care will be given. The benefits of finding a way to improve outcomes out-weighs the minimal risk.

9.5 Recruitment Strategy

Eligible participants will be identified through the inpatient and outpatient programs of the Eating Disorder Assessment and Treatment Program (EDATP) at CHOP. We will also recruit through CHOP satellite primary care facilities and online.

Adolescents enter our program through three primary pathways: through an outpatient nutrition and medical evaluation, through an outpatient multidisciplinary evaluation (psychology/psychiatry, nutrition, medical), or through hospitalization for medical stabilization of complications resulting from malnutrition. Screening for eligibility will occur either at an outpatient evaluation or during hospitalization for medical stabilization.

Potentially eligible patients identified (those in hospital with a diagnosis of anorexia or those presenting for an evaluation) will be contacted in advance of their appointments and informed they may be eligible for participation in research. If the family is interested, study procedures will be described to the family, including a brief review of inclusion and exclusion criteria. If the family is interested, consent to participate will be coordinated with the clinical intake. Assuming the adolescent is stable for outpatient treatment, they can enter the research study after the intake. The study staff will only collect private health information as it pertains to determining eligibility before consent, per CHOP IRB guidelines. Study staff will not collect any additional private health information without obtaining consent and HIPAA authorization first. As the Eating Disorder Program also has an inpatient program, the list of patients being treated as part of the

adolescent service will be reviewed daily. Eligible families will be contacted during the hospital stay via direct communication with study team members or by handouts in the informational packet provided to families at the beginning of the hospital study. Families who are interested can receive information and undergo consent and parts of the assessment while in hospital, should they desire. The remainder of the assessment, randomization, and beginning of treatment in the study protocol will begin after discharge from hospital.

In order to meet recruitment goals, we will augment the above procedures by advertising the study on the CHOP website as well as external websites such as FEAST. If a participant family reaches out to the study team based on internet announcements, tearpads, or fliers, general information about the study will be provided over the phone and, if interested, the family will have a limited phone screen to determine eligibility. If the adolescent and parents are eligible to participate, study staff will schedule the family for the baseline assessment. If the family is not receiving medical care in the EDATP, medical records will be requested from the PCP. The medical safety officer ([name]) will review the chart and make a recommendation regarding appropriateness for outpatient care.

Additionally, this study will appear in “This Week @ CHOP,” a segment in an internal newsletter made available to all CHOP employees. Interested families will be instructed to call study staff to determine eligibility, as outlined above.

Furthermore, the study team will be obtaining a list from CHOP’s Department of Biomedical Health Informatics (DBHI) of Medical Record Numbers (MRNs) of patients with an anorexia nervosa diagnosis within the last six months. Should they wish to, the DBHI could obtain this list of MRNs from the Recruitment Enhancement Core (REC), who has already pulled this data. Because we do not intend for the REC to act as an honest broker on our study team’s behalf, the REC will supply the DBHI with this information, which will then be supplied to our research team. When this list is obtained, the study team will communicate with eligible families to provide more information about this clinical trial if interested. We chose not to use the REC as an honest broker as we felt that it would potentially be overwhelming for families who have opted not to participate, are already involved in care, or otherwise not appropriate for the study. We will be able to compare the list of MRNs to those who have been screened and only approach those patients who have not been screened, if appropriate. With this approach, we hope to possibly identify adolescents who are being treated in primary care without behavioral health support.

